Physical activity (150 minutes of moderate intensity a week at least)	Eat large amounts of red meat (≥ 3 a week)
Eat fiber (around 30g a day benefits is greatest especially during adolescence)	Smoke (most risk during adolescence)
Follow a vegan diet though it is considered an incomplete diet	Use HRT (hormone replacement therapy) in menopause
Breastfeeding	

Differences between false positives and overdiagnosis

It is important to explain the differences between false positives and overdiagnosis.

A “positive result” is considered false when further examinations after mammography exclude breast cancer. “Overdiagnosis” instead means that there is a tumor, it is malignant but will not show itself in the rest of life. Unfortunately, it is still not possible to distinguish a tumor of this type so all are treated and the woman will never know what her situation really was.

The balance between benefits and harms

In medicine and healthcare a balance must be drawn up between positive effects (benefits) and negative ones (harm) to decide on the utility of an intervention. For mammography screening, the main benefit is the reduction of mortality due to breast cancer in the long-term, while the main harm is the risk of useless treatments.

Once the main results have been established, a balance must be set to gain an idea of their numbers: how many deaths due to breast cancer are avoided by screening programs? How much overdiagnosis is there, namely cases diagnosed in excess?

When the balance is positive, the health authorities can organize a screening program. Leading scientific authorities and societies, following different strategies, sometimes reach different conclusions on the benefits and especially on the harms.

How many fewer women die of breast cancer thanks to screening?	How many excess tumors are diagnosed by the screening?
The mortality reduction found by researchers is between 20% and 38%. The difference depends on the methods used to calculate these estimates, and no single one is universally considered better than another	Overdiagnosis ranges from 5% to 30%. The difference depends on the methods used to calculate these estimates, and no single one is universally considered better than another
How experts have calculated the mortality reduction due to breast cancer	How experts have calculated overdiagnosis

How are the rates of specific mortality reduction and overdiagnosis measured?

Current medical science bases its knowledge on the results of experimental or observational studies, on samples of the subset population. This rigorous method reduces the differences in opinion among physicians but does not eliminate them. The studies cannot give exact figures, but only a range of estimates that are probably close to the real figure (a bit like poll results for elections).

For mammography screening too, experimental and observational studies are analyzed. Experimental ones follow women for some time, dividing them into two groups: those who are take part in the periodical screening program; those who are not invited serve for “comparison”. Each woman is assigned by chance, as if by tossing a coin, to one group or the other. Later, mortality rates and breast cancer frequency in both groups are measured and compared. Experimental studies about mammography screening (8 clinical trials between 1963 and 1991) have evaluated around 500,000 women aged 40-74 in Europe and North America. The observational studies we consider examined screening programs in the 2000s and refer to women included in the screening programs organized according to the European guidelines who received the first invitation for screening, most of them aged 50 and 74 years.

To reach the most reliable conclusion, decisions are based on the results of many studies, called systematic reviews, that analyze together the results of experimental or observational studies, even if they have some different features. A method to decide what type of studies to include (for example only experimental, only observational, or both) is needed in order to weigh their different quality.

Screening programs started on the basis of experimental study results, in the early 1990s. The age for starting screening was debated: 40 years in the USA and more than 50 in Europe (usually up to 69). After that, several research groups conducted systematic reviews of all the studies using methods and strategies for quality assessment that have given different results, leading to debate among the researchers themselves.

For further reviews of results about mortality rates click [here](#); for those about overdiagnosis click [here](#).

Different estimates of the reduction of mortality due to breast cancer

The main reviews considered are the recent ones by the Cochrane collaboration (systematic review of experimental studies updated to 2013) and the Independent UK Panel (2012) that also evaluated only experimental studies; the Euroscreen Group included only observational studies based on European programs (2012) (see the sources).

The Cochrane review of experimental studies considers all invited women aged 40-74 and followed for 13 years, and estimates around a reduction of 20% of specific mortality for the whole series of studies, and around 0% omitting the less reliable studies.

The Independent UK Panel review, based on the same experimental studies and on all invited women aged 40-74 and followed for 13 years, also found a 20% mortality reduction, considering all the sufficiently reliable studies.

The Euroscreen review of European observational studies estimated a reduction of mortality due to breast cancer around 25% for women aged 50-69 in an organized mammography screening program. In addition, the reduction of mortality due to breast cancer for women regularly participating in a mammography screening program was about 38%.

Both the Cochrane and the UK Panel estimates are based on the same studies but used different methods and definitions. Those used by the Euroscreen group were similar to those used by the UK Panel even though the former examined observational studies, so the three reviews are not directly comparable. The Euroscreen appraisal answers to the question of what a woman would expect on deciding to take part in a European screening program, concerning the reduction of specific mortality. Therefore, the planners of the screening program you are invited to attend consider the Euroscreen estimates as most reliable to inform individual choices.

Different overdiagnosis estimates

The main reviews considered are the recent ones by the Cochrane collaboration (systematic review of experimental studies updated to 2013) and the Independent UK Panel (2012) that also evaluated only experimental studies; the Euroscreen Group included only observational studies based on European programs (2012) (see the sources).

To quantify overdiagnosis:

- From a general population perspective, the question is: “Out of all the women aged between 50 and 80 years who receive a diagnosis of breast cancer, what is the proportion overdiagnosed by the screening?”. To answer, the Euroscreen review in 2012, that included only observational studies, estimated that out of 1000 women aged 50 starting with a regular screening program, over the next 30 years 71 cancers will be found and 4 of them will be overdiagnosed and treated uselessly. That harm is around 5% in relative terms (measure A);
- From an individual perspective, the question is: “Participating in a screening program and receiving a diagnosis of tumor by the screening, what is the probability that it is an overdiagnosis?”. The estimate is around 10% (measure B)

The difference is due in particular to the fact that measure B considers only women diagnosed due to the screening.

In the Independent UK Panel’s review, based on three experimental studies, overdiagnosis reached about 11% when expressed as the proportion of all tumors found among the invited women (measure A), and 19% as the proportion of only tumors diagnosed during the active screening period (measure B).

The Cochrane review, based on several experimental studies (ages 40-74), analyzed the excess of treatments (mastectomies and conservative procedures), indirectly reaching an estimate of overdiagnosis around 30%, including - as the denominator - all tumors diagnosed in the control group at the end of the follow-up.

The Cochrane and UK Panel’s estimates are both based on experimental studies but used different methods and definitions. Those used by the Euroscreen group were similar to those used by the UK Panel but analyzed observational studies, so the three reviews are not directly comparable.

Who we are

This project is coordinated by IRCCS Istituto di Ricerche Farmacologiche Mario Negri in collaboration with Lega Italiana Lotta contro i Tumori-Firenze, Zadig Agenzia di Editoria Scientifica, GISMa Gruppo Italiano Screening Mammografico and with Prevenzione Serena di Torino, dell’Unità Operativa Centro Gestionale Screening di Palermo e dell’Istituto per lo Studio e la Prevenzione Oncologica di Firenze.

The project is funded by AIRC, the Italian Association for Cancer Research- IG2015-17274.

Istituto di Ricerche Farmacologiche Mario Negri IRCCS: [name], [name], [name]

Zadig Agenzia di Editoria Scientifica: [name], [name]

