Sponsor Representative	[name] Laboratory of Medical Research and Consumer Involvement Department of Public Health IRCCS Istituto di Ricerche Farmacologiche “Mario Negri”
Background and rationale	Breast cancer is the most common cancer in women. In Italy, women are invited to a population-based mammography screening programme for the first time at the age of 45 or 50 years. Results from randomised controlled trials, observational studies, and systematic reviews continuously fuel the debate on the balance on benefits (reducing breast cancer mortality) and harms (overdiagnosis, overtreatment) of mammography screening. Physicians, policy makers, as well as laypeople or patient associations agree on the need to inform women about the potential benefits and harms in order to allow an aware decision process. Decision aids are an effective way to support lay people in their decisions about health.
Objectives Primary	To assess the effect of an interactive web decision aid on informed choice – measured through knowledge, attitudes and intentions concerning breast cancer screening – comparing the decision aid with a standard information provided via web (web brochure).
Secondary	
• To compare the participation rate in breast cancer screening between intervention (web decision aid) and control group (web brochure).• To compare the satisfaction between the intervention (web decision aid) and the control group (web brochure) on information in terms of length, quantity, clarity, balance, helpfulness in making decision and women willingness to recommend it to other women.• To measure the time spent on web pages between the intervention (web decision aid) and the control group (web brochure). Only for the intervention group, to measure number of pages visited, frequency of access, level of information and level of detail reached on the main topics.

	
 • To compare the decisional conflict process between the intervention and the control group.
Study design	Multi-centre, randomised, controlled study
Number of centers	More than 3
Number of patients	8160 women will be invited in order to reach 816 patients evaluable for primary endpoint.
Target population	The women aged 45-69 or 50-69 years new invited to the regional screening programmes of the participant centers .

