4. STUDY DESIGN

This is a multi-centre, randomised, controlled study to assess the efficacy of the high quality information approach driven by a multilevel web platform. The screening centres involved are based in different cities of Italy. In accordance with the target age of the women invited to the regional screening programmes, the present study will include 45-69 years or 50-69 years old new invited women. The eligible women will be invited to participate to the study through an ad-hoc letter by the belonging screening centre. The letter, delivered 30-45 days before of the standard screening program invitation letter, will provide information regarding the study and how to access to the web platform.

The women will be randomized to receive:

- Web platform with a multilevel information and an aid for the decision to be taken (whether participating or not to the mammography screening organised for free by the Italian Health Service). (Intervention group).
- Web platform with a standard brochure (Control group). This standard brochure represents a combination of the best information available from participant centre' brochures, see the

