6.2 Inclusion criteria

- Women aged 45-69, according to the target age of the screening centres involved;
- New invited women in mammography screening programme.

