14. APPENDIX

14.1 Appendix 2: Control group – Web brochure

Screening is a public health program where healthy population, at an age judged to be at risk, is invited by local health system to undergo free preventive examinations, such as mammography, Pap test or fecal occult blood test.

Screening may help anticipate cancer diagnosis and treatment, allowing less invasive surgical interventions. For breast cancer screening every woman, between 50 and 69 years of age, receives a letter of invitation with a fixed appointment to carry out a free mammography every 2 years. Scientific research has proven that screening for breast, uterus, and colorectal cancers can save many lives.

MAMMOGRAPHY

Currently, for women aged between 50 and 69, mammography is the most effective test to detect tumors that are not yet symptomatic and are not palpable.

It is a radiograph of the breast that uses very low X-ray doses.

To obtain a clear result it is necessary to compress the breasts. This compression can be bothersome or may cause slightly pain, but lasts a few seconds. The radiographer is highly qualified and the equipment used is technologically advanced and controlled. All this makes it possible to obtain images of excellent quality.

For greater security on the diagnosis, the images are examined separately by two radiologists to ensure greater accuracy. However, like all tests, it is not foolproof: in some cases, it may not recognize a tumor that is there or suspect a non-existent tumor.

WHY A MAMMOGRAPHY?

In Italy, breast cancer is the first cancer among women due to incidence, i.e. number of new cases of breast cancer in a year. It is the most common cancer among women, with tens of thousands new cases and 11,000 deaths. The mammography performed regularly allows an early diagnosis, before the onset of symptoms, and the possibility of intervening with a high probability of definitive recovery. Data support that, for every 1000 women aged between 50 and 69 years who regularly perform mammography, 7-9 lives are saved within 20 years.

WHAT ARE THE LIMITS OF THE MAMMOGRAPHY?

- In general, every 100 women who had a mammography, about 5 must repeat the exam or undergo in-depth examinations. For 4 of them it is actually a "false alarms", as the in-depth analyses exclude the presence of a tumor (the so-called false positives). The disadvantage is mainly represented by the anxiety that a woman can experience in such situation.

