It is only possible to estimate the reduction of mortality due to breast cancer by the mammography screening program, and of extra tumor diagnosis (overdiagnosis).

Participation in the screening provides the following benefits and harms to be assessed before taking a decision:

- Reduction of mortality due to breast cancer
- Overdiagnosis
- Less invasive treatments
- False positives or false negatives
- Radiation damage
- Inconvenience of the examination

What happens in the next 30 years?

What happens at 1000 women aged 50 in the next 30 years

Out of 1000 women aged 50 who regularly participate in a mammography screening program, in

the next 30 years:

- 71 will receive a diagnosis of breast cancer (discovered by screening or from clinical symptoms)
- 12 will die from breast cancer
- 8 will not die from breast cancer thanks to the screening
- 4 will receive overdiagnosis and useless treatments

If the same 1000 women are followed without a mammography screening program:

- 67 will receive a diagnosis of breast cancer
- 20 of them will die due to the breast cancer

In other words, in the next 30 years:

Some women will die from breast cancer anyway: 12 of the 1000 who participate in the mammography screening program compared to 20 if the screening program did not exist. Therefore 8 out of 1000 women are saved from death due to breast cancer; 4 of the 1000 women receive a diagnosis and are then treated uselessly for tumors detected by the screening that would probably never emerge. If there is no mammography screening program, there is no overdiagnosis and only evident tumors are treated.

At what age is mammography screening recommended?

In Italy the mammography screening program is carried out every two years for women aged 50-69 because there is impressive evidence of the reduction of mortality.

In some Italian regions (Emilia Romagna, Piedmont and Tuscany), the mammography screening program is extended to women aged from 45 to 49 every year and between 70 and 74 every two years. For these age bands the demonstration of the utility of screening is considered sufficient, though the balance of the related benefits and harms is still debated.

The European Code against Cancer (2015) confirmed the recommendation for women aged 50-69 to do the organized mammography screening and, in certain circumstances, also women aged 45-49 and 70-74.

The risks related to radiation

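### The control brochure describes screening only for ages 50-69 every 2 years, although the trial enrols women from 45 and the decision aid covers ages 45-49

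*Combined protocol and SAP*

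**What the plan says.** **Eligibility.** Section 6.2 admits "Women aged 45-69, according to the target age of the screening centres involved", restricted to women newly invited to the programme. Section 4 says that "the present study will include 45-69 years or 50-69 years old new invited women". The synopsis puts the first invitation in Italy at one of two ages: "women are invited to a population-based mammography screening programme for the first time at the age of 45 or 50 years".

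**Control material.** Section 4 describes one brochure for all control women: "This standard brochure represents a combination of the best information available from participant centre' brochures". No version by age or centre is described. Its text is in Section 14.1 (labelled Appendix 2). On who is invited, it says "For breast cancer screening every woman, between 50 and 69 years of age, receives a letter of invitation with a fixed appointment", and it gives the interval as "to carry out a free mammography every 2 years". The statement on test effectiveness and the lives-saved figure (7-9 per 1000 within 20 years) are also limited to ages 50-69. The false-positive and overdiagnosis figures carry no age. Ages 45-49 are not mentioned.

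**Intervention material.** The decision aid (Section 14.2, labelled Appendix 1) first gives the national offer as ages 50-69 every two years. It then says that in Emilia Romagna, Piedmont and Tuscany "the mammography screening program is extended to women aged from 45 to 49 every year", and that the balance of benefit and harm at these ages is still debated. Its home page tells each woman that her invitation will arrive within weeks and refers to lower mortality at her age. A later screen says that women of her age are regularly invited.

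**The concern.** The primary objective is to compare an interactive decision aid with standard web information. That contrast is clean when both materials describe the same offer and differ in depth, format and decision support. For a woman of 45 to 49 they do not describe the same offer. The brochure sets out a programme for women older than she is, at an interval that the aid does not give for her age. The aid includes her.

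Attitude and intention, two of the three components of informed choice, and later attendance could all respond to whether the material appears to concern the reader. A difference between arms in this age group would then mix the effect of the decision aid with the effect of an omission in the control text. Apart from any bias, eligible women would be asked to make an informed choice using a description of a different age group's programme.

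**Working it through.** The main check is a comparison of the texts, since the plan gives no figure for this point.

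| Item | Eligibility | Control brochure | Decision aid |
|---|---|---|---|
| Age range invited | 45-69 or 50-69, by centre | 50-69 | 50-69 nationally; 45-49 and 70-74 added in three regions |
| Interval | not stated | every 2 years | every 2 years at 50-69; every year at 45-49 |
| Evidence at 45-49 | not applicable | none given | sufficient, but balance debated |
| Reader treated as in the invited group | yes | only if aged 50-69 | yes, on the home page and a later screen |

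The arms conflict with each other, and the brochure conflicts with the eligibility rule, on age and on interval. Section 9.2 plans an unadjusted chi-square test with no analysis by age or centre. Section 4.2 describes 1:1 allocation without stratification.

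**Who could be affected.** Only centres inviting from 45 matter. Section 14.2 names screening centres in Turin, Palermo and Florence; Turin is in Piedmont and Florence in Tuscany. The synopsis foresees more than 3 centres, and neither recruitment by centre nor age within centre is given. The share of women aged 45-49 therefore has to be assumed.

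**Direction on informed choice.** With adequate knowledge, a woman counts as informed if attitude (24 or more is positive) and intention agree (Section 5.1). Only the top two intention answers are positive; I treat the other three as negative. If the brochure moves a control woman from likely to unsure:

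- attitude stays at 24 or more: consistent becomes inconsistent, and informed choice is lost;
- attitude was already below 24: inconsistent becomes consistent, and informed choice is gained;
- attitude falls below 24 as well: she stays consistent, with no change.

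No knowledge item asks about the invited age or the interval at 45-49, so the knowledge component gives no clear route.

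**Size, on assumed values.** With share *f* of women aged 45-49 and a net change of *d* points in younger controls only, the overall difference moves by *f* × *d*:

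| *f* | *d* = 2 | *d* = 5 | *d* = 10 |
|---|---|---|---|
| 10% | 0.2 | 0.5 | 1.0 |
| 25% | 0.5 | 1.25 | 2.5 |
| 50% | 1.0 | 2.5 | 5.0 |
| 67% | 1.3 | 3.4 | 6.7 |

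The design difference is 10 points (Section 9.1.3).

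**Participation.** Suppose two-thirds of the 408 controls, 272 women, are 45-49. A loss of 10 percentage points among all of them is 27.2/408 = 6.7 points. At the 40% control participation in the plan's own table, 272 × 0.40 = 109 would attend; deterring 10% of those attenders loses 10.9 women, and 10.9/408 = 2.7 points. The first result is above the 5-point row of that table and the second below it, so the answer depends on an assumption that the documents do not settle.

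**What an age split could show.** For 50% versus 60%, two-sided 5%, power is about Φ[(0.10 − 1.96·s₀)/s₁], with s₀ = √(2 × 0.55 × 0.45/n) and s₁ = √((0.25 + 0.24)/n) for n per arm. At n = 272, s₀ = 0.0427, s₁ = 0.0424 and power is 65%. At n = 136, s₀ = 0.0603, s₁ = 0.0600 and power is 38%. With that 272/136 split, the difference between the two age-specific effects has standard error √(0.49/272 + 0.49/136) = 0.0735, so its 95% interval is about ±14 points.

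**The case against.** The strongest reply is that no woman relies on the brochure alone. Each enters through a letter from her own screening centre, sent 30-45 days before the standard invitation (Section 4), so she has reason to know that the centre counts her as eligible. The brochure nowhere says that screening is confined to ages 50-69. The comparator is also deliberately standard information assembled from the centres' leaflets; fuller content is part of what the aid is tested for, and rewriting the brochure to resemble the aid would erode the contrast. Finally, the text on 45-49 is one of 16-20 screens that a woman may leave early, and the aid's main outcome figures and the numerical knowledge items refer to women aged 50 in both arms.

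Much of this stands. The letter should soften any effect, and age-specific numbers for 45-49 are lacking in both arms. It does not remove the conflict. The aid's home page addresses the reader's own age group before she reaches any detailed screen. Follow-up comes 7-10 days after randomisation, so a woman who registers promptly answers before the programme's invitation arrives. The brochure is the trial's own composite, so correcting its description of the offer is open to the sponsor and leaves the rest of the comparator intact.

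A reader might infer that the mismatch biases both informed choice and participation in favour of the aid. The documents do not support that. Informed choice can be lost, gained or unchanged when intention falls, as shown above, and the aid's remark that the balance at 45-49 is debated could lower attitude, intention and attendance in the intervention arm.

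**Conclusion.** The point holds as an inconsistency between eligibility, control material and intervention material that adds an unintended difference between arms for women aged 45-49. It applies only to centres inviting from 45, and assumes that the brochure is shown there as printed.

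Size and direction cannot be derived. The range of 0.2 to 6.7 points is an illustration on assumed shares and effects. It would also be tempting to read two-thirds of controls as affected and a participation shift above 5 points as expected. That share assumes exactly three equally recruiting centres, with every woman in two of them aged 45-49, and the shift assumes a loss of 10 percentage points; deterring 10% of attenders gives 2.7 points instead. The sample size of 816 is untouched. The correction is worth making because it is small and specific and removes an avoidable ambiguity in interpretation.

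**What to change.** Before launch, reconcile the brochure, the eligibility criteria and the decision aid on invited age range and interval. The sponsor, with the centres, should determine the correct programme description for each. For centres inviting from 45, the brochure should include the woman's own age group and say that its age-limited figures come from women aged 50-69. The rest of the standard content should stay as it is.

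Record age, from the centre lists if they hold it (Section 10.3 does not say) and otherwise as a baseline item, since the Appendix 3 questionnaire as printed shows none. Pre-specify a descriptive table of informed choice and participation by arm for 45-49 and for 50 or older, with an arm-by-age interaction estimate and its confidence interval. Label it exploratory with limited power. If recruitment has already begun, the table remains possible provided age can be obtained.

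Cost: a few sentences of web text that need ethics committee approval (Sections 11.3 and 11.6), possibly one questionnaire item, and one extra table. The brochure would depart slightly from the centres' existing leaflets.
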